6.1.6 Interim analysis

As documented in the protocol, Amendment Version 3.0, there was an interim analysis of data to check the sample size assumptions based on approximately 75 enrolled pre-period patients. A separate report was completed on the interim analysis. No further interim analysis is planned. The output that was produced for the interim analysis is denoted in the table shells with a J following the title.

6.1.7 Subgroup analyses

Currently no subgroup analyses are planned for this study. If applicable, analyses will be repeated for subgroups of interest. Exploratory analyses will be performed such that selected outputs are repeated by sites if needed.

6.1.8 Statistical software

All analyses will be performed by statisticians/data analysts, in accordance with Good Programming Practices guidelines, and will follow the statistical analysis plan outlined in this document, including the corresponding table shells referenced herein. All analyses will be performed using [REDACTED]. Table, listing and figure output will be generated and delivered as Adobe Acrobat (PDF) files.

6.1.9 Quality Control

All output will be validated and/or QC'd according to Mapi standard operating procedures. Output tables and figures will be double programmed and undergo statistical review prior to being sent to Allergan.

6.2 Statistical Methods

Descriptive analyses will be performed as follows: for continuous variables, patient counts, percentages, means, 95% confidence intervals (CI) of the means, standard deviations (SD), medians, first (25th percentile) and third (75th percentile) quartiles, minima and maxima, and number missing (where applicable) will be reported. For categorical variables, patient counts and percentages for each category, as well as number missing (where applicable), will be reported. Where applicable, summaries for continuous variables will include frequencies and percentages for discrete categories (e.g., number of ED visits: 0, 1, 2, and so forth).

For applicable categorical measures of baseline characteristics (including demographics, infection characteristics at baseline, comorbid conditions reported at baseline, and prior healthcare resource utilization within past 3 months), the pre-period cohort will be compared with the post-period cohort using chi-square tests or Fisher's exact tests, as appropriate. Differences in proportions of the pre-period and post-period and their corresponding asymptotic 95% confidence interval (CI) will be reported, where applicable. For applicable continuous variables, two-sided Student's t-tests and Mann-Whitney U tests will be used where normality assumptions have, and have not, been met, respectively. Where applicable, differences in descriptive statistics, proportions, and corresponding 95% CI will also be provided between the pre- and post-periods.

Hypothesis testing is specified for outcomes in section 6.2.5. All statistical testing, if done, will be two-sided at the significance level of 0.05 with the exception of the primary outcome, which will be tested with a one-sided Pearson chi-square test for proportion difference with a significance level of 0.05. Secondary outcomes will be analyzed predominantly by descriptive analyses and by number of incidences where applicable. Planned analyses are presented in Sections 6.2.5.2. All planned hypothesis testing and any

unplanned deviation from hypothesis testing for secondary outcomes will be purely exploratory, as adequate power will not likely be present to determine statistical significance. There will be no adjustments made for multiple comparisons.

6.2.1 Patient Disposition

The number and percentage of enrolled and FAS patients, number and percentage of patients who complete the study, and number and percentage of patients who discontinue from the study and reason for withdrawal will be summarized in tables for all patients and repeated by site. This information will also be reflected in a data listing including the patient's enrollment date, early discontinuation or study completion date, and date of death, if applicable. Patients who are excluded from the enrolled set due to not meeting inclusion or exclusion eligibility criteria will be summarized in listings.

Although tables and listings will not reflect screen failures captured with enrollment logs, the clinical study report (CSR) text will address the approximate number of screen failures and the most common reasons for screen failure.

6.2.2 Study Site Characteristics

Study site characteristics will be summarized in a table by the pre-period and post-period. Specifically, number of patients and overall percentages will be described for study site characteristics (skin infection, pneumonia, diabetic foot infection and infective endocarditis admissions relative to all-cause hospital admissions) in a table and proportions amongst the pre-period versus the post-period will be compared by a 2-sample Z-test.

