2.1.2 Rationale of study design

The design of this study allows for a site to understand baseline treatment patterns for ABSSSI, then after this period, to implement an institution-level intervention (i.e., each site contributes study subjects to both treatment arms), as opposed to concurrently across sites (i.e., each site contributes study subjects to a single arm). Use of this design removes site-level variables as a source of potential confounding and enables comparisons of the new critical pathway to usual care in the same setting(s) and similar subject populations.

[figure not shown]
The study is designed in a “pragmatic” fashion (i.e., minimal inclusion/exclusion criteria, which will enable an examination of the impact of the new critical pathway under “real-world” conditions, with good generalizability/applicability to clinical practice.

[figure not shown]
In order to account for temporal trends, sites will also be required to generate data, or reports, on admission rates during the pre- and post-period for other infections, including diabetic foot infections (currently part of exclusion criteria) and pneumonia (a non-skin infection). This will aid in supporting a true difference in outcomes during the pre-period versus the post-period based on the new critical pathway for ABSSSI.

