3.0 Study Design

This study will employ a "pre-post" pragmatic design, which will consist of both a pre-period, or an observational baseline period, and a post-period, or an interventional period. The pre-period and post-period will consist of independent groups of patients. During the pre-period, each participating site will implement the first component of the critical pathway through implementation of guideline-based criteria to identify patients at the point of care in the ED, obtain informed consent, and monitor enrolled patients. Sites will initiate treatment for ABSSSI with "usual care," defined as site- or physician-specific antibiotic treatment of ABSSSI with coverage for a known or suspected Gram-positive infection (e.g., vancomycin, linezolid, and daptomycin) to each study patient who meets all inclusion and exclusion criteria. Blinding of treating physician to patient enrollment in the study during the pre-period will ensure unbiased provision of usual care. During the post-period, for all patients who provide informed consent and are subsequently enrolled, each participating site will additionally implement the second component of the new critical pathway, use of dalbavancin, at the point of care in the ED to each study patient who meets all inclusion and exclusion criteria. Sites are expected to transition to the post-period at the enrollment of 50 patients. There is no expectation for all sites to transition to the post-period at the same time.

For both periods of interest, patient follow-up spans the period beginning on the day of study enrollment and ends 44 days thereafter, which incorporates an initial care period of 14 days (reflecting the 10–14-day period during which most antibiotics are anticipated to be required for care of ABSSSI) and a subsequent “follow-up” period of 30 days. Study measures will be collected as described in the protocol and will be based on medical records, unless otherwise indicated.

A schedule of assessments is provided in Appendix A. Follow-up visits will be scheduled for approximately 24 hours after enrollment (post-period only), 48–72 hours after enrollment (post-period only), 14 days after enrollment (both periods), and 44 days after enrollment (both periods). Any additional visits to the visit schedule below will be at the discretion of the patient and treating physician.

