4.0 Study Measures

4.1 Study Site Characteristics

Study site characteristics consist of counts of all-cause admissions, skin infections, pneumonia, diabetic foot infection, and infective endocarditis recorded at each site. These will be collected in paper admission logs monthly or bimonthly from the sites. These will be entered into an Excel spreadsheet by Mapi’s Clinical Operations team, which will then be brought into [REDACTED] for analysis.

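### The pooled 2-sample Z-test on the admission logs ignores site and month, so it can report a background change that no site had, or hide one that every site had.

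*SAP*

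**What the plan says.** Protocol 2.1.2 gives the logs their purpose: "In order to account for temporal trends, sites will also be required to generate data, or reports, on admission rates" for diabetic foot infection and pneumonia, so that a pre/post difference in the trial outcome can be credited to the pathway.

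SAP 4.1 describes the data: counts at each site for several infections and for all causes. "These will be collected in paper admission logs monthly or bimonthly from the sites".

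SAP 6.2.2 gives the analysis: "number of patients and overall percentages will be described for study site characteristics". Each percentage is the count for one of four infection groups divided by the hospital's admissions for any reason. The test follows: "proportions amongst the pre-period versus the post-period will be compared by a 2-sample Z-test". The section names no site stratification, month term or allowance for extra variation. The level comes from SAP 6.2: "All statistical testing, if done, will be two-sided at the significance level of 0.05 with the exception of the primary outcome". That section also says "There will be no adjustments made for multiple comparisons".

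On timing, SAP 3.0 says "There is no expectation for all sites to transition to the post-period at the same time". It gives an enrolment trigger for leaving the pre-period but no per-site length for the post-period, and study duration is left open.

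Protocol section 5 says the comparison of study outcomes will account for site. SAP 6.2.2 carries no such provision for the logs.

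**The concern.** The question in Protocol 2.1.2 is whether background admissions changed over time at these hospitals. The null hypothesis of a pooled Z-test is different: that all pre-period and all post-period admissions, pooled over sites and months, are independent draws with the same share. The two come apart in two ways.

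- **Site mix.** If hospitals differ in their pneumonia or diabetic-foot share, and a hospital contributes a larger part of one pool than of the other, the pooled shares differ although no hospital changed.
- **Month-to-month variation.** The binomial standard error counts only sampling variation among admissions. With hospital-wide denominators it is very small, so ordinary fluctuation in monthly shares can exceed it.

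This is the only analysis in the readable SAP that serves the temporal-trend check. A spurious background change could cast doubt on a real pathway effect. A mix shift that cancels a real within-site change could give false reassurance.

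**Working it through.** **Inputs from the documents.** About 8 sites (Protocol section 6 and synopsis); two-sided 0.05 (SAP 6.2); four infection counts, each over all-cause admissions (SAP 6.2.2). **Not in the documents:** log counts, site shares, window lengths and monthly variance. Every value used for these below is an assumption.

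**Step 1. The plan's own level.** Under the test's own assumptions the size is 2(1 − Φ(1.96)) = 0.050. Simulation with 8 sites, a common share and no extra variation gave 4.2 to 5.4%. Four such tests, if independent, give 1 − 0.95⁴ = 18.5% for at least one false signal even when each is exact.

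**Step 2. Site mix alone.** Take two equal-sized sites with constant shares of 2% and 4%. Each logs 6 months before the switch; afterwards the first logs 4 months and the second 6.
- Pre: 0.5 × 2% + 0.5 × 4% = 3.0%
- Post: 0.4 × 2% + 0.6 × 4% = 3.2%

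With N admissions per period, Z = 0.002 / √(0.031 × 0.969 × 2/N).

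| N per period | Expected Z | Chance of p < 0.05 |
|---|---|---|
| 5,000 | 0.58 | 8.9% |
| 20,000 | 1.15 | 21.1% |
| 60,000 | 2.00 | 51.5% |

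The reverse also happens. If both sites truly fell by 6.25% (to 1.875% and 3.75%), the pooled post share would be 0.4 × 1.875% + 0.6 × 3.75% = 3.0%, which shows no change.

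**Step 3. Month-to-month variation alone.** If a site's monthly share varies around p with coefficient of variation c, the variance of a monthly count from n admissions is the binomial variance times 1 + (n − 1)pc²/(1 − p). With n = 1,500 and p = 3.5%:
- c = 10%: 1 + 1,499 × 0.035 × 0.01/0.965 = 1.54; true size 2(1 − Φ(1.96/√1.54)) = 11.5%
- c = 20%: 1 + 1,499 × 0.035 × 0.04/0.965 = 3.17; true size 2(1 − Φ(1.96/√3.17)) = 27.1%

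**Step 4. Both together, by simulation.** 8 sites, 500 to 2,500 admissions per site-month, shares 2 to 5%, pre windows 3 to 9 months, no within-site change, 3,000 runs per cell. The last column is a site-stratified Mantel-Haenszel test with its variance multiplied by the Pearson dispersion of the site-month counts.

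| Post window | Monthly CV | Pooled Z | Plain Mantel-Haenszel | Stratified, dispersion-scaled |
|---|---|---|---|---|
| Equal to pre | 0 | 4.9% | 4.9% | 4.4% |
| Within 25% of pre | 0 | 7.7% | 5.0% | 4.6% |
| Independent, 3–9 months | 0 | 26.2% | 5.3% | 4.9% |
| Equal to pre | 10% | 12.4% | 12.4% | 6.5% |
| Equal to pre | 20% | 27.5% | 27.5% | 5.9% |
| Independent, 3–9 months | 10% | 30.6% | 12.3% | 6.0% |

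Separate runs gave 7 to 8% for windows within 25%, 26 to 28% for independent windows, and up to 14% and 29% for the two equal-window rows with monthly variation.

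**Step 5. Where the effect is smaller.** Pooled Z in the same set-up:
- Small hospitals (200 to 800 per month): 12.4% with independent windows and no monthly variation; 14.6% with equal windows and 20% monthly variation.
- Rare condition (share 0.3 to 0.8%): 9.9% and 10.2% in the same two cells.
- Both return to 5 to 6% when post length is within 25% of pre and there is no extra variation.

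**The case against.** **The inflation may be slight.** Each site applies the same eligibility criteria in both periods, so its two windows may well be similar in length. Within 25%, site mix adds only 2 to 3 points to the 5% level; within 10% the rate is about 5.7%. This stands, and it rules out saying that the test will report a false change. It does not answer the month-to-month component, which inflates the size even with equal windows.

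**Seasonality.** A reader might add a seasonal cycle and get far higher rejection rates (49 to 72% with a 20% amplitude, depending on the set-up). Those are not false positives in the sense that matters here. If pre and post fall in different seasons, background admissions did differ, and a control series should show it. The primary test in SAP 6.2.6.1 has no seasonal term, so taking season out of the control could make the check look clean while the primary comparison keeps the difference.

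**The consequence is limited.** A reader might infer that a faulty log test undermines the primary result. Nothing in the documents ties this p-value to the primary test or to a decision rule. The spurious differences are also small in absolute terms: with independent windows and no monthly variation, the median was 0.11 percentage points and the 95th percentile 0.35, on a share of about 3.5%. A reader who sees the percentages is unlikely to set that against a planned 38% versus 23%. This stands, and it limits the priority of the point.

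**The plan leaves room to adapt.** SAP 6.0 allows modified analyses and SAP 6.1.7 allows by-site output if needed, but neither commits to a method for the logs. Pooling is itself a reading of the overall percentages in SAP 6.2.2; the table shells are in a separate file, and the aggregation rule in SAP 6.1.1 names outcomes and baseline characteristics only.

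**Conclusion.** The concern holds in this form: read as pooled, the planned test does not match the within-site question, and its standard error omits variation that these logs can be expected to have. It can report a change when no site has one, or hide a real one. How often cannot be known from the documents. Under the main assumptions above, the nominal 5% test runs from about 5% (equal windows, no extra variation) to 26–28% (unrelated windows) or 12–29% (equal windows, 10 to 20% monthly variation). Inflation is smaller for rare infections and small hospitals, and nearly absent when site weights match and months are stable. The documents do not support saying that a false signal is certain, that seasonal differences are errors of the test, or that the primary analysis is invalid. The point is worth correcting because the logs are the stated check on temporal trends and the data for a better analysis are already collected.

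**What to change.** In SAP 6.2.2, replace the pooled Z-test with a within-site comparison of the log counts by reporting interval.

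- For each control infection, fit a quasi-Poisson model with site fixed effects, a period indicator and log all-cause admissions as offset, or use a site-stratified test. Either way, scale the standard error for overdispersion.
- Report the within-site post/pre ratio with its 95% CI, plus by-site estimates.
- Do not rely on plain Mantel-Haenszel: it removes the site-mix error but still rejected 12 to 28% of the time under 10 to 20% monthly variation with equal windows. The dispersion-scaled version stayed between about 4 and 8% in all cells run.
- Keep seasonal differences in the main control estimate, because the primary comparison keeps them. A seasonally adjusted version may be shown as a sensitivity analysis.
- Present skin-infection admissions separately, since they overlap the target condition and are not a control.

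The cost is a paragraph of SAP text, a revised table shell and a little programming, with no new data. The drawback is wider intervals for the control infections.

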6.2.3 Demographic and Baseline Characteristics

All demographic data will be summarized in tables and listings by the pre-period and post-period for the enrolled and FAS populations. Descriptive statistics will be summarized for age (in years), height at baseline (in cm), weight at baseline (in kg) and BMI at baseline (in kg/m²). Patient counts and percentages will be summarized for age (e.g., <20 years, 20-29 years, 30-39 years, etc.), race/ethnicity, gender, employment status (e.g., employed, full time, part time, unemployed), admission source (e.g., from home, LTC, SNF, nursing home), and insurance information. This information will be captured in listings with date of birth.

All baseline characteristics for comorbid conditions will be summarized by the pre-period and post-period for the FAS population by patient counts and percentages in tables and include the following measures: morbid obesity, myocardial infarction, congestive heart failure, peripheral vascular disease, cerebrovascular disease, dementia, chronic obstructive pulmonary disease, connective tissue disease, peptic ulcer disease, mild liver disease, moderate or

severe liver disease (Child- Pugh Class B and C), hemiplegia, lymphedema / chronic venous stasis, diabetes mellitus (with and without end-organ damage), moderate to severe chronic kidney disease (e.g., actual measurement and GFR, estimated measurement and GFR, unknown measurement), leukemia and remission status, lymphoma and remission status, metastatic solid tumor and remission status, alcohol abuse, drug abuse including illicit needle use, protein calorie malnutrition, immuno-compromising conditions such as HIV, AIDS, receiving ≥ 20 mg Prednisone daily (or therapeutically equivalent steroid), receiving TNF inhibitors, receiving any other immune modulating medication including biologics, and receiving chemotherapy. The Charlson Comorbidity Index will be derived and described by descriptive statistics. All data will be reflected in listings.

Healthcare resource utilization within the 3 months prior to study enrollment will be reported in tables by the pre-period and post-period for the FAS population. Number of patients and percentages of occurrences (e.g., none, any, 1, 2, ≥ 3) and primary reasons for the following will be reported: hospitalizations, admissions to the ICU, surgical interventions, and ED or outpatient visits. Descriptive statistics will also be presented for these variables. Additionally, number of patients and percentages of coded diagnoses terms will be reported for hospitalizations and admissions to the ICU and number of percentages for specified surgical procedures. The number and percentages of patients with minor and major surgical procedures will be displayed. The table will also reflect the number and percentages of patients with dialysis use, prior medications used for chronic diseases, prior use of antibiotics, and wound care for the presenting infection. Listings for hospitalizations will capture the type of visit, primary reason for visit, primary diagnosis (coded and verbatim), admission date and time, discharge date and time, ICU admissions for hospitalizations and discharge disposition. Prior antibiotic medications will be reported in a listing and will include start date and end date, medication named (coded and verbatim), reasons for prescription, dose with units and frequencies, route, and reason for discontinuation.

6.2.4 Infection Characteristics at Baseline

Patient counts and percentages will be summarized by the pre-period and post-period for the FAS population for primary infection type, purulent drainage from primary lesion, primary lesion location, primary lesion size ($75\text{cm}^2 - 150\text{cm}^2$, $\geq 150\text{cm}^2$) number of additional lesion (e.g., 0, 1, 2, ≥ 3), fever, SIRS (met i.e., ≥ 2 criteria present, by individual criteria, and by number of criteria met) and recurrent/ABSSSI infection in prior 6 months. Descriptive statistics will be summarized for primary lesion size. Differences in infection characteristics between the pre- and post-period will be assessed using statistical significance testing. All of the aforementioned variables will be reflected in listings.

6.2.5 Care Pathways Following the Initial Episode of Care

The care pathways of patients following the initial episode of care will be summarized using descriptive statistics for the FAS population by the pre- and post-periods and by whether or not the patient was admitted. Variables to summarize will be: Dalvance use, time (hr) in ED at initial episode, time (hr) admitted under observation status, total LOS (days) during the initial hospitalization, total time in ICU (days) during the initial hospitalization, discharge status, and discharge disposition.

6.2.6 Outcomes

6.2.6.1 Primary Outcomes

Primary Outcome: Hospital Admission Rate at Initial Episode of Care

Hospital admission at initial episode of care will include infection-related stays upon discharge from the index ED visit (derived and described in Appendix B). Tables will reflect patient counts and percentages for hospital admission (yes, no) at the initial episode of care by the pre-period and post-period for the FAS population. Summary rows will be repeated by site.

The primary analysis will consist of hypothesis testing using a one-sided, two-sample Pearson chi-square test for proportion difference with a normal approximation. An appropriate alternative method will be selected if a major violation to an assumption is present.

Because the baseline characteristics of the pre-period may differ from those of the post-period, a secondary analysis using a multivariate logistic regression analyses will be implemented. This model will assume mutual independence between the sites.

Clinically relevant baseline characteristics of interest for the adjusted analysis include the following variables: age, gender (Male, Female), race (White/Caucasian, Black or African American, Other), employment status (Full-Time, Part-Time, None), insurance plan type (Private commercial plan, Government funded, Uninsured, Other), Charlson Comorbidity Index, lesion surface area (<75cm², =>75 cm² – 150 cm², >150 cm²), infection type (Wound infection, Cellulitis/erysipelas, Abscess), prior health resource use (Yes, No, Unknown), prior antibiotic treatment failure (Yes, No, Unknown), presence of SIRS criteria (<2 or >=2), presence of recurrent infection in prior 6 months (Yes, No, Unknown), any health resource use in prior 3 months (Yes, No, Unknown), as well as is patient was immunocompromised (Yes, No, Unknown). Patients will be defined as immunocompromised if they have evidence of any of the following at baseline: Connective tissue disease, diabetes mellitus, leukemia, or malignant lymphoma. Categorical variables will be collapsed where possible. The primary predictor variable will be a pre/post-period indicator, and potentially other selected characteristics will be forced into the model based on clinical rationale and distributions observed in the

data (specifically imbalance between the pre- and post-periods). The stepwise selection of variables in the logistic regression will be done. The retention criteria in the model will be set as 0.1. The final model results will be presented in a table.

